### **8.1.2.4. Clinical Global Impression – Improvement (CGI-I) at Day 2**

CGI-I (1-7 scale) at Day 2 will be treated as a continuous variable with scores compared using ANCOVA, with treatment as the variable of interest, and with baseline SSS, age group, baseline CGI-I score, baseline neurotoxicity, and country as covariates. The model will be used to estimate the effect of treatment on CGI-I scores at Day 2. The comparison of varespladib-methyl to placebo (varespladib-methyl vs. placebo) will be tested at a 5% two-sided significance level;

the corresponding p-value and 95% two-sided confidence intervals will be presented.

A sensitivity analysis will add completion of initial dose of antivenom prior to initiation of study drug as a covariate. Subgroup analyses will estimate the treatment effect separately for pediatric and adult patients, for patients with and without clinically significant neurotoxicity, for patient who have and have not completed an initial dose of antivenom prior to randomization, for the U.S. and for India, for each snake type (viper, elapid, and unknown), and for patients for whom the time from bite or symptom onset to receipt of study drug was <5 hours and  $\geq 5$  hours.

### 8.1.3. SAS Code for Primary and Key Secondary Efficacy Endpoints

Sample SAS code is provided below for these analyses using standard ADaM terminology; where TRT01PN is a numeric treatment group variable (0,1), AGEGR2BL is the two-group age strata (5 to 11 years, 12 to 17 years), NEUROBL is the indicator variable for baseline neurotoxicity (No, Yes), and ANTIVBLG is a three-group categorical variable for type of antivenom prior to baseline (Indian Polyvalents, CroFab, and ANAVIP). Note that PROC MIXED reduces to ANCOVA when no REPEATED statement is used. The LSMEANS option within will provide the treatment effect estimates of interest.

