### **6.1.2. Adjustments for Covariates**

The comparison of the primary and secondary efficacy endpoints between the varespladib-methyl and placebo groups for the primary efficacy analysis will be adjusted for four variables: (1) baseline SSS composed of the pulmonary, cardiovascular, hematologic, renal, and nervous system sections treated as a continuous variable; (2) age group treated as a dichotomous variable (age 5-17 vs. age  $\geq$ 18 years); (3) baseline neurotoxicity (SSS neurological system subscore) treated as a dichotomous variable (0-1 vs.  $\geq$ 2); and (4) Country (U.S. vs. India). Because we anticipate low numbers of patients in the two pediatric age group strata, we have collapsed these two strata into a single group (age 5-17) for the purpose of data analysis. A sensitivity analysis for the primary and key secondary endpoints will include a fourth covariate: completion of the initial dose of antivenom prior to initiation of study drug (Yes or No).

The mixed model for repeated measurements (MMRM) will be adjusted for baseline SSS, baseline neurotoxicity, age group, completion of the initial dose of antivenom prior to initiation of study drug, and scheduled timepoint of assessment. It will also include terms for treatment-by-time interaction and baseline score-by-time interaction.

The Cox model to estimate the hazard ratios for all-cause mortality will be adjusted for baseline SSS, baseline neurotoxicity, age group, and completion of the initial dose of antivenom prior to initiation of study drug.

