For the second key secondary endpoint, total antivenom administration, if the patient has complete data on antivenom administration through Day 3, then no change will be made to the total antivenom administered. This decision reflects the fact that in clinical practice in the U.S. and India, antivenom administration after 48 hours is uncommon. If the patient is missing data prior to Day 3, then the treatment of missing data will depend on the reason for missingness. If the patient has been discharged from the hospital, then no changes will be made to the available total amount of antivenom administered. If the patient has missing data prior to Day 3 and has not been discharged from the hospital or is transferred to another hospital, we will review each case and based on the patient's SSS will determine if the patient met criteria of additional antivenom. If the patient did meet criteria for additional antivenom, then we will assume a single additional dose was given to the patient, with the number of vials in this dose corresponding to the standard treatment dose in the region where the patient is receiving care.

For the third key secondary endpoint, AUC of the NPRS through Day 3, multiple imputation will be used to replace missing scores based on country, baseline age, gender, baseline NPRS scores, treatment assignment, and available post-baseline NPRS scores. More details on the multiple imputation process are provided in [Section 6.1.4.1](#) below.

For the fourth key secondary endpoint, CGI-I at Day 2, multiple imputation will be used to model missing values; with more details in [Section 6.1.4.1](#) below.

Individuals who cannot respond to patient-reported assessments due to severity of snakebite envenoming will be given a score corresponding to the worst score available in the assessment. Specific assessments and unable to respond scores are:

- PSFS = 0 (Unable to perform activity)
- PGIC = 10 (Feel much worse)
- Grip Strength = 0

A tipping point analysis will be conducted as a sensitivity analysis to handle missing data for the primary efficacy endpoint. More details are provided in [Section 6.1.4.3](#) below.

For the key secondary efficacy endpoints, a sensitivity analysis to handle missing data will be conducted only if results cannot be calculated for more than 10 study participants. In this case, the nature of the sensitivity analysis will be determined on review of the data.

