#### 6.1.4.1. Multiple Imputation

The multiple imputation (MI) procedures for the primary and key secondary endpoints are described below.

For the primary analysis, missing data not due to mortality, and not addressed by the averaging rules above, will be imputed using the following regression-based multiple imputation model.

The following imputation algorithm will be applied to each SSS subscore separately, then the primary outcome SSS score will be derived.

1. The first step is to understand the pattern of missingness. In order to perform the multiple imputation, a monotone missing pattern must be achieved. For example, if there exist values for baseline and Day 2 visits, but missing values for the Day 1 (8-10h) visit, Markov-Chain Monte-Carlo (MCMC) method will be used to impute the small amount of missing data that may be missing at the intermediate visits that is required to make the missing data pattern monotone before applying the multiple imputation algorithm. This method uses a non-informative Jeffreys prior to derive the posterior mode from the expectation-maximization (EM) algorithm as the starting values for the MCMC method. This MCMC method will use seed of 432832. To avoid values that could not be observed in practice, imputed values will be constrained to be integers in the range of 0 to 3 or 0 to 4 by convention to align with the scale of the questionnaire. A total of 10 imputations will be done in the MCMC step.
2. Once the monotone pattern is achieved, the next step is to implement the imputation algorithm. For this, the Predictive Mean Matching method (PMM) will be used. This method is particularly helpful if the normality assumption is violated. For subjects with complete data up to a particular visit, a PMM model will be fit that includes the outcome at that visit as the dependent variable; and as independent variables gender, treatment assignment, study site, and non-missing scores using a seed of 931428. This process will be repeated 15 times, resulting in a total of 150 complete analysis datasets.
3. For each completed dataset, any necessary derived variables will be computed. Then the ANCOVA model will be performed for the 6 and 9 hour average SSS score. The results will be combined into one MI inference (LS mean, associated 95% CI, and p-value) using PROC MIANALZE as illustrated (Ratitch et al., 2013).

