#### **Primary Efficacy Endpoint**

```
Proc univariate data=ADEF; /*visually inspect distribution*/
  Where PARAM="Primary Outcome SSS Score";
  Class AVISIT;
  Var CHG;
  Histogram;
  Run;

Proc mixed data=ADMI plots=studentpanel alpha=0.05;
  By _imputation_;
  Where PARAM="Primary Outcome SSS Score" and AVISIT="Average of 6 and
    9 hours";
  Class TRT01PN(ref='0') AGEGR2BL(ref='5 to 11 years')
    NEUROBL(ref='No') COUNTRY(ref='India');
  model CHG = BASE TRT01PN AGEGR2BL NEUROBL COUNTRY;
  lsmeans TRT01PN / cl pdiff;
  run;
proc mianalyze data=Estimates alpha=0.05;
  modeleffects estimate;
  stderr StdErr;
  run;
/*code for sensitivity analyses using initial antivenom dose as a
covariate, compressed SSS score, and component subscores are similar*/
```

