### **Key Secondary Efficacy Endpoint #4, CGI-I**

```
Proc mixed data=ADMI alpha=0.05;  
Where PARAM="CGI-I Score" and AVISIT="Day 2";  
Class TRT01PN(ref='0') AGEGR2BL(ref='5 to 11 years')  
NEUROBL(ref='No') COUNTRY(ref='India');  
Model AVAL = TRT01PN SSSBL AGEGR2BL NEUROBL COUNTRY;  
lsmeans TRT01PN / cl pdiff;  
run;  
proc mianalyze data=Estimates alpha=0.05;  
modeleffects estimate;  
stderr StdErr;  
run;
```

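### The sample SAS code in SAP 8.1.3 does not implement the models the SAP text specifies for the fixed-sequence tests, and the text leaves the NPRS-AUC covariates unsettled

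*SAP*

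**What the plan says.** **Age.** SAP 6.1.2 has "age group treated as a dichotomous variable (age 5-17 vs. age" 18 and over, and explains that the two paediatric strata were collapsed because few children are expected. Sections 8.1.2, 8.1.2.1, 8.1.2.2 and 8.1.2.3 use the same split. The legend that opens 8.1.3 instead says "AGEGR2BL is the two-group age strata (5 to 11 years, 12 to 17 years". The primary block reads "Class TRT01PN(ref='0') AGEGR2BL(ref='5 to 11 years", and the SSS-AUC, NPRS-AUC and CGI-I blocks use the same reference label. The antivenom block uses a 5-to-17 label for the same variable.

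**CGI-I pooling.** SAP 6.1.4 states: "For the fourth key secondary endpoint, CGI-I at Day 2, multiple imputation will be used to model missing values". Section 6.1.4.1 applies the primary method to CGI-I: impute, "resulting in a total of 150 complete analysis datasets", fit each one, then combine. The primary, SSS-AUC and NPRS-AUC blocks carry a `BY _imputation_` statement. The CGI-I block reads the imputed data and calls PROC MIANALYZE but has no such statement.

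**Baseline covariates.** For primary and secondary endpoints alike, SAP 6.1.2 adjusts for "baseline SSS composed of the pulmonary, cardiovascular, hematologic, renal, and nervous system sections treated as a continuous variable". Section 8.1.2.3 names baseline NPRS for NPRS-AUC and does not list baseline SSS. Section 8.1.2.4 names both baseline SSS and baseline CGI-I for CGI-I at Day 2. The CGI-I block has "Model AVAL = TRT01PN SSSBL AGEGR2BL NEUROBL COUNTRY", and the NPRS-AUC block has the same right-hand side.

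**Antivenom block.** The legend codes treatment as 0/1 and neurotoxicity as No/Yes, and defines a three-type variable, ANTIVBLG. The block uses treatment reference 2, neurotoxicity level N, and a variable ANTIVBL with level N. Section 8.1.2.2 asks for prior antivenom as Yes/No.

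**The concern.** These blocks cover all five tests in the fixed sequence, which SAP 4.1 treats as formal tests in a confirmatory study. The code was added to the SAP on purpose (Document History, version 3.0), and SAP section 14 says the document is meant for regulatory submission. The introduction to 8.1.3 calls it sample code, but nothing says whether text or code prevails where they differ.

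A programmer or regulator who compares the two finds different models for the same alpha-protected test. In most places the text shows which one is meant. For NPRS-AUC it does not, so the covariate set could be chosen after the data are seen. Prespecification is meant to prevent that choice.

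**Working it through.** **Design figures.** The sample size is not affected. A two-sample t-test with difference 1.1, SD 1.75 and two-sided 0.05 (SAP 3.2) has 85.4% power at 47 per arm, which agrees with the stated 94 patients and 85%.

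**(a) Age.** No two-level AGEGR2BL satisfies all five blocks.

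| If AGEGR2BL is built as | Label `5 to 11 years` (four blocks) | Label `5 to 17 years` (antivenom block) | Adults |
|---|---|---|---|
| Legend of 8.1.3 | exists | does not exist | no level |
| Text, 6.1.2 and 8.1.2 | does not exist | exists | have a level |

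The legend does not match the randomization strata in SAP 3.5 either (5 to <11 and 11 to <18): an 11-year-old is in the older stratum there but in the younger group in the legend. The code has to be edited on any reading.

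**(b) CGI-I pooling.** Section 6.1.4.1 gives 10 MCMC imputations and 15 predictive-mean-matching imputations for each: 10 x 15 = 150, as stated. Without the BY statement, PROC MIXED fits one model to all 150 copies and passes one estimate on. The between-imputation variance has divisor m - 1. With m = 1 that is zero, so there is nothing to pool.

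The standard error of that single fit follows directly. The printed model has 6 parameters: intercept, treatment, baseline SSS, age, neurotoxicity and country. Take N subjects with complete data and residual sum of squares RSS, and let A be the treatment element of the inverse cross-product matrix for one copy.

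- Correct variance: A x RSS/(N - 6).
- Stacked variance: (A/150) x 150 RSS/(150N - 6) = A x RSS/(150N - 6).
- SE ratio: sqrt[(N - 6)/(150N - 6)].
- N = 94: sqrt(88/14094) = 0.0790.
- N = 110: sqrt(104/16494) = 0.0794.

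So the stacked standard error is about 0.08 of the correct one. With missing values the correct standard error also has a between-imputation part, which lowers the ratio a little further.

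**(c) Baseline covariates.**

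| Source | Baseline SSS | Endpoint's own baseline |
|---|---|---|
| NPRS-AUC: 6.1.2 (all primary and secondary endpoints) | yes | not listed |
| NPRS-AUC: 8.1.2 (change-from-baseline models) | yes | yes |
| NPRS-AUC: 8.1.2.3 | not listed | yes |
| NPRS-AUC: code block | yes | omitted |
| CGI-I: 8.1.2.4 | yes | yes |
| CGI-I: code block | yes | omitted |

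For CGI-I the specific text is unambiguous and only the code differs. For NPRS-AUC the three text sections give three covariate sets. Section 8.1.2 does not settle it, because an AUC is not strictly a change from baseline.

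**(d) Antivenom block.** Its covariates (baseline SSS, age with a 5-17 level, neurotoxicity, prior antivenom, country) agree with 8.1.2.2. It conflicts only with the legend: reference 2 against 0/1, N against No, and ANTIVBL, which the legend does not define, against ANTIVBLG, which no block uses.

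**The case against.** The best reply is that this is schematic sample code. No block contains the step that creates the Estimates data set which PROC MIANALYZE reads, so the code was never meant to run as printed. The age split is stated consistently in the text with a reason, and the antivenom block already uses it. The CGI-I block calls PROC MIANALYZE, so pooling was plainly intended. The antivenom covariates match the text. Most of this stands, and it makes (a), (b) and (d) corrections of legend and code rather than doubts about the intended analysis.

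It does not dispose of (c). A rule that the text prevails would settle CGI-I but not NPRS-AUC, where the text disagrees with itself. The word sample also suggests that the code is subordinate without saying so.

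Two stronger readings are tempting. A reader might infer that adults would fall out of the primary analysis and its power would collapse. That needs the variable to be built from the legend against 6.1.2, and the loss would show at once in the number analysed. Its size would depend on a paediatric share that the documents do not give. A reader might also infer that the CGI-I test would give false positives at a high rate. That needs an unpooled PROC MIXED p-value to be reported, contrary to 6.1.4.1, at the last gate of the sequence. How often that gate is reached depends on powers the documents do not give for the key secondary endpoints. If the primary null is true, the first gate still holds the chance of any false claim in the sequence to 5%.

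**Conclusion.** The mismatches are real and should be corrected before lock. The legend and four blocks have the wrong age variable. The CGI-I block cannot produce the pooled result the text requires. Two blocks omit a baseline covariate named in the text, and the NPRS-AUC model is not uniquely prespecified. The antivenom block has a legend and coding conflict for which no effect is claimed.

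The one supported size is conditional: if all 150 copies were fitted together, the standard error would be about 0.08 of the correct value (complete data, 94 or 110 subjects, the six-parameter model as printed). This is a reason never to report such a p-value. It is not a forecast of the trial's error rate. Leaving out a baseline covariate in a randomized comparison costs precision and does not inflate type I error; the cost depends on correlations that the documents do not give. Sample size, power and the order of testing are unchanged.

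**What to change.** Before database lock and while blinded:

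- Define AGEGR2BL as 5-17 against 18 and over in the 8.1.3 legend, and use those labels in every block.
- Add `BY _imputation_` to the CGI-I block.
- Add baseline NPRS to the NPRS-AUC block and baseline CGI-I to the CGI-I block.
- Have the sponsor decide whether baseline SSS stays in the NPRS-AUC model, and make 6.1.2, 8.1.2, 8.1.2.3 and the code agree.
- Use one coding for treatment, one for neurotoxicity and one prior-antivenom variable (Yes/No, as in 8.1.2.2) in the legend and all blocks.
- State in 8.1.3 that the SAP text governs wherever it differs from sample code.

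The cost is a few edits to text and code and at most one covariate degree of freedom in each of the NPRS-AUC and CGI-I models. No new data are needed.

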#### **Primary Efficacy Endpoint**

```
Proc univariate data=ADEF; /*visually inspect distribution*/
  Where PARAM="Primary Outcome SSS Score";
  Class AVISIT;
  Var CHG;
  Histogram;
  Run;

Proc mixed data=ADMI plots=studentpanel alpha=0.05;
  By _imputation_;
  Where PARAM="Primary Outcome SSS Score" and AVISIT="Average of 6 and
    9 hours";
  Class TRT01PN(ref='0') AGEGR2BL(ref='5 to 11 years')
    NEUROBL(ref='No') COUNTRY(ref='India');
  model CHG = BASE TRT01PN AGEGR2BL NEUROBL COUNTRY;
  lsmeans TRT01PN / cl pdiff;
  run;
proc mianalyze data=Estimates alpha=0.05;
  modeleffects estimate;
  stderr StdErr;
  run;
/*code for sensitivity analyses using initial antivenom dose as a
covariate, compressed SSS score, and component subscores are similar*/
```

#### **Key Secondary Efficacy Endpoint #1, SSS-AUC**

```
Proc mixed data=ADMI alpha=0.05;
  By _imputation_;
  Where PARAM="Primary Outcome SSS-AUC through Day 7" and AVISIT="Day
    7";
```

```
Class TRT01PN(ref='0') AGEGR2BL(ref='5 to 11  
years') NEUROBL(ref='No') COUNTRY(ref='India');  
model AVAL = TRT01PN SSSBL AGEGR2BL NEUROBL COUNTRY;  
lsmeans TRT01PN / cl pdiff;  
run;  
proc mianalyze data=Estimates alpha=0.05;  
modeleffects estimate;  
stderr StdErr;  
run;
```

### **Key Secondary Efficacy Endpoint #2, Antivenom**

```
proc logistic data = adeff descending;  
where paramcd = 'ANTIVG';  
class TRT01PN(ref = '2') AGEGR2BL(ref = '5 to 17 years')  
NEUROBL(ref = 'N') ANTIVBL(ref = 'N') COUNTRY(ref='India')  
/param = ref;  
model AVALC = TRT01PN SSSBL AGEGR2BL NEUROBL ANTIVBL COUNTRY /  
link = clogit aggregate scale = none;  
run;
```

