#### **3.2. Sample Size and Power**

The sample size for this phase 2 study was determined by a formal power calculation based on the primary efficacy endpoint. This study was powered at 85% to detect a statistically significant (2-sided alpha = 0.05) treatment effect. The assumptions are the following:

- 2-sided alpha level 5%
- Power 85%
- Randomization ratio 1:1
- A minimum difference in the change from Baseline to the average at 6- and 9-hour pulmonary, cardiovascular, hematologic, renal, and nervous system subscores of the SSS of 1.1 points and a standard deviation 1.75

A sample size of 94 patients will provide 85% power to identify a difference of 1.1 in the primary outcome (two-sided alpha = 0.05). The sample size has been calculated using nQuery 8.

The randomization scheme will be 1:1 stratified by age group (5 to < 11, 11 to < 18, and  $\geq$  18 years old) and by the presence or absence of neurotoxicity (SSS nervous system subscore of 0–1 or  $\geq$  2) at Baseline, resulting in 6 strata in total.

Because we anticipate up to 15% withdrawal through the end of the study, we requested permission to enroll up to 110 patients to ensure adequate power for secondary outcomes.

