#### **8.1.2.2. Total Differential Antivenom Requirement from Baseline through Day 28**

The total number of vials of antivenom administered will be analyzed using a proportional odds logistic regression with three ordered categories. For each type of antivenom administered, the number of vials of antivenom from baseline through Day 28 will be categorized as low, medium, or high. Cutoffs for these categories are based on recommendations regarding treatment for each antivenom type as well as a review of available blinded data.

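### The SAP 8.1.3 code pools the imputed ANCOVAs with near-infinite degrees of freedom (true size about 5.3%, not 5%) and does not secure the Low < Medium < High order for antivenom

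*SAP*

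**What the plan says.** SAP 8.1.3 introduces the code with "Sample SAS code is provided below for these analyses using standard ADaM terminology".

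- **Pooled ANCOVAs.** SAP 6.1.4.1 produces 150 completed datasets (10 × 15) and combines the ANCOVA results. For the primary endpoint, SSS-AUC, NPRS-AUC and CGI-I, the combining step is "proc mianalyze data=Estimates alpha=0.05", which is given only an estimate and its standard error. No `EDF=` option appears, and the text is silent on degrees of freedom for the pooled tests. The CGI-I model also lacks the `BY _imputation_` line that the other three have.
- **Antivenom.** SAP 8.1.2.2 says vials will be "analyzed using a proportional odds logistic regression with three ordered categories", named low, medium and high. SAP 6.1.7.7 uses Low, Med and High. The code is "proc logistic data = adeff descending" followed by "model AVALC = TRT01PN SSSBL AGEGR2BL NEUROBL ANTIVBL COUNTRY". It shows no `ORDER=` option, format or numeric recode, and the SAP nowhere says what `AVALC` contains. SAP 6.1.4.1 states that this endpoint is not multiply imputed, so the degrees-of-freedom point does not reach it.

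**The concern.** These are the only worked implementations of the alpha-protected tests in a study that SAP 4.1 calls confirmatory. The primary test opens the fixed sequence, so any anti-conservatism there matters in principle, even if small.

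Antivenom is the second key secondary endpoint, and in SAP 8.1.2 its failure closes the sequence to NPRS-AUC and CGI-I. A cumulative-logit model needs its levels in the intended order. With zero vials in the middle, the two cuts are Medium against {Low, High} and {Medium, Low} against High. The contrast of no antivenom with any antivenom is never formed. SAP 8.1.2 also words each gate as rejection of the null with no condition on direction, so a significant result the wrong way round would open the next gate.

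**Working it through.** SAS was not run. Two software defaults are assumed: `PROC MIANALYZE` without `EDF=` takes the complete-data degrees of freedom as infinite, and `PROC LOGISTIC` sorts a character response alphabetically unless told otherwise.

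**The plan's own figure.** SAP 3.2 states "A sample size of 94 patients will provide 85% power", for "subscores of the SSS of 1.1 points and a standard deviation 1.75", two-sided 5%, 1:1. The normal formula gives 2 × (1.960 + 1.036)² × (1.75/1.1)² = 45.4, so 46 per arm (92). The two-sample t-test gives 47 per arm (94) with power 85.4%, an exact match. Allowing for 15% withdrawal, 94/0.85 = 110.6, against 110 enrolled.

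**Pooled degrees of freedom**

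1. The primary model has 6 parameters: intercept, baseline, treatment, age group, neurotoxicity, country. Residual df are 94 − 6 = 88 or 110 − 6 = 104.
2. Without `EDF=`, the df are (m − 1)/λ², where m = 150 and λ is the between-imputation share of the variance. The documents do not give λ. At an assumed 5%, 149/0.05² = 59,600. At 15%, 149/0.15² = 6,622. Both are effectively infinite.
3. With `EDF=` set to ν₀, the Barnard–Rubin df are 1/(1/ν_m + 1/ν_obs), where ν_m is the step 2 value and ν_obs = (ν₀ + 1)/(ν₀ + 3) × ν₀ × (1 − λ).

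| N | ν₀ | λ | df with EDF | Critical value with / without EDF | True size without EDF |
|---|---|---|---|---|---|
| 94 | 88 | 0 | 88 | 1.987 / 1.960 | 5.32% |
| 94 | 88 | 5% | 81.7 | 1.989 / 1.960 | 5.34% |
| 94 | 88 | 15% | 72.4 | 1.993 / 1.960 | 5.38% |
| 110 | 104 | 0 | 104 | 1.983 / 1.960 | 5.27% |
| 110 | 104 | 5% | 96.8 | 1.985 / 1.960 | 5.29% |
| 110 | 104 | 15% | 85.6 | 1.988 / 1.960 | 5.32% |

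The λ = 0 rows drop the small-sample factor and show the plain ANCOVA t-test. Interval width is off by 1.983/1.960 = 1.012 to 1.987/1.960 = 1.014 in those rows, a little over 1%. A correct p of 0.050 would be reported as about 0.046 to 0.047.

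4. The CGI-I code has a larger gap. If the imputed dataset holds all 150 copies, a fit without `BY _imputation_` stacks them and understates the standard error by about √150 ≈ 12. Also, SAP 8.1.2.4 includes baseline CGI-I, giving 7 parameters and 110 − 7 = 103 df. The code omits that covariate.

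**Antivenom order**

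If `AVALC` holds Low, Med or Medium, and High, the sort is High, Low, Medium. `DESCENDING` reverses this to Medium, Low, High, which leaves Low in the middle. Size was checked with 100,000 simulated trials per row: the rank score test for the proportional-odds model, treatment as the only term, 55 per arm. The placebo mixes and the true odds ratio of 0.50 for higher use are assumptions.

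| Placebo Low/Medium/High (%) | Power, planned order | Rejection rate, alphabetical order | Estimated odds ratio, alphabetical order |
|---|---|---|---|
| 30/45/25 | 49% | 6% | 1.07 |
| 50/30/20 | 45% | 5% | 1.00 |
| 20/30/50 | 49% | 26%, nearly all in the wrong direction | 1.58 |
| 60/25/15 | 40% | 6% | 0.93 |
| 33/33/33 | 50% | 10%, mostly in the wrong direction | 1.26 |

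With equal arms, the rejection rate is 4.9% to 5.1% in either order.

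**The case against.** The case against has four parts.

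- **Status of the code.** It is labelled sample code and cannot be production code. The `Estimates` dataset is never created, treatment is defined as 0/1 but the antivenom step uses reference 2, and the age reference level differs between steps. The text in SAP 8.1.2.2 is correct and should govern. This lowers the certainty that the faults reach the final analysis. It does not remove them, because the text says nothing that would correct either one.
- **Conditionality of the ordering point.** A reader might infer that the antivenom categories are certainly misordered. The documents do not support that: order-preserving stored values such as 1, 2, 3 would make the code right, and `DESCENDING` would then model higher use as intended. This stands in full. What remains is that the code does not secure the order.
- **Dependence on the assumed mix.** At a true odds ratio of 0.33 with 55 per arm, alphabetical order leaves only 6% to 8% power for mixes from 20/50/30 to 40/40/20 (84% to 86% in the planned order). For 15/35/50 the estimate reverses to 1.94. But for 20/70/10 it keeps about 28% power in the right direction, and for 30/65/5 about 58%. The loss is not total in every case.
- **Size of the pooling error.** It is small, and SAP 6.1.4 imputes the primary endpoint only if gaps remain after averaging and blinded investigator scoring. If nothing is missing and pooling is skipped, the ordinary t-test applies. If the pooling step is run anyway, between-imputation variance is zero and the unadjusted df are still unlimited. The effect grows in small subgroups (6.9% at 15 df, 7.8% at 10 df), but SAP 8.1.1 and 8.1.2 keep those outside the gatekeeping.

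**Conclusion.** Both faults stand in limited form. The pooling code is anti-conservative for the primary endpoint and for the first, third and fourth key secondary endpoints: size about 5.3% instead of 5%, intervals about 1% too narrow, and a changed gate decision only for a correct p between 0.050 and about 0.054. For CGI-I the missing `BY _imputation_` is the bigger fault, since pooling has no meaning until it is added.

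The antivenom code leaves the planned order unprotected. If the SAP's labels are what is stored, the planned model is not fitted, the odds ratio loses its meaning, and power is lost or the effect reversed to a degree set by the category mix.

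A reader might conclude that the alpha-protected p-values are wrong across the board. That goes too far: misordering leaves type I error near 5%, and the pooling error is about 0.3 percentage points. These conclusions rest on the two SAS defaults named above, on the assumed λ, and, for the antivenom figures, on assumed mixes, assumed odds ratios and a model without covariates.

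**What to change.** Make the following changes before unblinding, since a later change of response order that alters an odds ratio would look data-driven.

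1. Add `EDF=` to each `PROC MIANALYZE` call, equal to that model's own residual degrees of freedom (subjects minus parameters): 104 for 110 subjects and 6 parameters, 103 for CGI-I with baseline CGI-I included as SAP 8.1.2.4 states, and the subgroup's own value in each subgroup run.
2. Add `BY _imputation_` to the CGI-I model.
3. For antivenom, model a numeric response coded 0 = Low, 1 = Medium, 2 = High. State that coding in SAP 6.1.7.7 and check the printed response profile.

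The cost is a few lines of code and pooled intervals about 1% wider in the full set.
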